3.2.4 APF12

The APF12 will be defined as the Kaplan-Meier estimate of PFS (per investigator assessment according to RECIST v1.1 criteria) at 12 months.

3.2.5 ORR

ORR is defined as the proportion of patients with measurable disease at baseline who have at least 1 visit response of CR or PR. If any patients do not have measurable disease at baseline then the analysis of ORR will exclude these patients, so that the denominator is a subset of the SS who have measurable disease at baseline. Data obtained up to progression or last evaluable assessment in the absence of progression will be included in the assessment of ORR.

However, any CR or PR which occurred after a further anti-cancer therapy was received will not be included in the numerator for the ORR calculation (where the SS with measurable disease will be the denominator).

ORR (%) = No. of patients with CR or PR before further anti-cancer therapy after first dose /No. of a subset of SS patients with measurable disease *100, results round to 1 decimal place.

3.2.6 DoR

Duration of response is only calculated for patients who have a best overall tumor response of CR or PR before further anti-cancer therapy after first dose.

Duration of response will be defined as the time from the date of first documented response until the date of PD or death in the absence of disease progression. The end of response should coincide with the date of PD or death from any cause used for the PFS endpoint. The time of the initial response will be defined as the date of tumor assessment for the first response of PR or CR.

If a patient does not progress following a response, then his/her duration of response will use the PFS censoring time.

DoR (months) = (Date of event or censoring – Date of first documented CR or PR before further anti-cancer therapy after first dose + 1) /30.4375, results round to 1 decimal place.

3.2.7 OS

Overall survival is defined as the time from the date of first dose of study treatment until death due to any cause. Any patient not known to have died at the time of analysis will be censored based on the last recorded date on which the patient was known to be alive. The possible last recorded date could be found from visits, AEs, concomitant medication, cancer therapy, vital signs, physical examination, lab test, study drug exposure, survival status survey and disposition of patient.

OS (months) = (Date of death or last recorded date on which the patient was known to be alive - date of first dose of study treatment + 1) /30.4375, results round to 1 decimal place.

3.2.8 OS12

The OS12 will be defined as the Kaplan-Meier estimate of OS at 12 months.

3.2.9 Incidence of AEs, SAEs, AESIs and AEs leading to treatment discontinuation

An AE is the development of an undesirable medical condition (other than progression of the malignancy under evaluation) or the deterioration of a pre-existing medical condition following or during exposure to a pharmaceutical product, whether or not considered causally related to the product. An undesirable medical condition can be symptoms (eg, nausea, chest pain), signs (eg, tachycardia, enlarged liver), or the abnormal results of an investigation (eg, laboratory findings). In clinical studies, an AE can include an undesirable medical condition occurring at any time, including run-in or washout periods, even if no study treatment has been administered.

The term AE is used to include both SAEs and non-serious AEs.

AEs will be collected from time of signing of informed consent throughout the treatment period and including the follow-up period up to 90 days after the last dose of durvalumab treatment.

An SAE is an AE occurring during any study phase (i.e. treatment, follow-up), that fulfils one or more of the following criteria:

- results in death

- is immediately life-threatening
- requires in-patient hospitalization or prolongation of existing hospitalization
- results in persistent or significant disability/incapacity
- is a congenital abnormality or birth defect
- is an important medical event that may jeopardize the patient or may require medical
- intervention to prevent one of the outcomes listed above

An AESI is one of scientific and medical interest specific to understanding of the Investigational Product and may require close monitoring and rapid communication by the investigator to the sponsor.

The AESIs reported in the AstraZeneca-sponsored durvalumab studies are defined as AEs that have a likely inflammatory or immune-mediated pathophysiological basis resulting from the mechanism of action of durvalumab and requiring more frequent monitoring and/or interventions such as corticosteroids, immunosuppressants, and/or endocrine therapy. Endocrine therapies include standard endocrine supplementation, as well as treatment of symptoms resulting from endocrine disorders (for example, therapies for hyperthyroidism include beta blockers [e.g., propranolol], calcium channel blockers [e.g., verapamil, diltiazem], methimazole, propylthiouracil, and sodium perchlorate, infusion-related reactions and hypersensitivity/anaphylactic reactions).

An AstraZeneca medically qualified expert after consultation with the Global Patient Safety Physician has reviewed the AEs of interest and identified which MedDRA preferred terms contribute to each AESI. A further review will take place prior to Database lock (DBL) to ensure any further terms not already included are captured within the categories. Specific terms(PT and SOC) will be defined in an external file.

AEs leading to treatment discontinuation including AEs leading to durvalumab permanently discontinuation and AEs leading to EP permanently discontinuation.

The incidence rate of AEs/SAEs/AESIs/AEs leading to treatment discontinuation (%) = No. of patients with at least one AEs/SAEs/AESIs/AEs leading to treatment discontinuation / No. of patients in SS *100, results round to 1 decimal place.

3.3 Other safety variables

[REDACTED]

[REDACTED]

[REDACTED]

[REDACTED]

3.3.2 Lab test

Lab test will be measured at screening and every visit during the study. The parameters to be measured are variables in hematology, clinical chemistry and urinalysis.

Hematology parameters include absolute neutrophil count (ANC), absolute lymphocyte count (ALC), haemoglobin, platelet count (PLT) and total white cell count (WBC).

Clinical chemistry parameters include albumin, lipase, alkaline phosphatase (ALP), magnesium, alanine transaminase (ALT), potassium, amylase, sodium, aspartate transaminase (AST), total bilirubin (TBil), bicarbonate, total protein, calcium, TSH, free T3 and free T4 (reflex testing only if TSH is abnormal), chloride, creatinine, gamma glutamyl transferase (GGT), urea or blood urea nitrogen (depending on local practice), glucose and lactate dehydrogenase.

Corrected calcium product will be derived during creation of the reporting database using the following formula:

$$\text{Corrected calcium (mmol/L)} = \text{Total calcium (mmol/L)} + ([40 - \text{Albumin (g/L)}] \times 0.02)$$

Urinalysis parameters include bilirubin, ketones, blood, pH, colour and appearance, protein, glucose and specific gravity.

3.3.3 Vital signs, weight and BMI

Vital signs will be monitored at screening and at every visit during the study. Parameters include pulse rate, respiratory rate, systolic blood pressure (SBP), diastolic blood pressure (DBP), height, weight, BMI and body temperature.

3.3.4 Physical examinations

At screening and each visit during the treatment period, a complete physical examination will be performed and include an assessment of the following: general appearance, respiratory, cardiovascular, abdomen, skin, head and neck (including ears, eyes, nose and throat), lymph nodes, thyroid, musculo-skeletal (including spine and extremities) and neurological systems.

3.3.5 ECGs

Resting 12-lead ECGs will be recorded at screening and as clinically indicated throughout the study. The results include overall evaluation and its clinical significance.

3.3.6 ECOG PS

ECOG PS will be assessed at screening and at every visit during the study. The result will range from 0 to 5, while higher score represents a severer case / worse performance status.

3.3.7 Pregnancy test

Pregnancy test will be performed in women of childbearing potential only. A urine or serum pregnancy test is acceptable. Women of childbearing potential are required to have a pregnancy test within 7 days prior to the first dose of study drug and then every 4 weeks. The result will be negative or positive.

3.3.8 Potential Hy's law case

Patients experiencing a Hy's Law incident will be tabulated and details will be included in by-patient listings. Hy's Law incidents are those cases where a patient shows an AST or ALT $\geq 3 \times$ ULN together with total bilirubin $\geq 2 \times$ ULN. Please refer to Appendix B of the CSP for further instructions.

The following summaries (n, %) of the laboratory data will be used to identify cases of Hy's law: Elevated ALT, AST, and total bilirubin during the study

- ALT $\geq 3x - \leq 5x$, $> 5x - \leq 8x$, $> 8x - \leq 10x$, $> 10x - \leq 20x$, and $> 20x$ upper limit of normal (ULN) during the study
- AST $\geq 3x - \leq 5x$, $> 5x - \leq 8x$, $> 8x - \leq 10x$, $> 10x - \leq 20x$, and $> 20x$ ULN during the study
- Total bilirubin $\geq 2x - \leq 3x$, $> 3x - \leq 5x$, $> 5x$ ULN during the study
- ALT or AST $\geq 3x - \leq 5x$, $> 5x - \leq 8x$, $> 8x - \leq 10x$, $> 10x - \leq 20x$, and $> 20x$ ULN during the study
- ALT or AST $\geq 3x$ ULN and total bilirubin $\geq 2x$ ULN during the study (Potential Hy's law): The onset date of ALT or AST elevation should be prior to or on the date of total bilirubin elevation

Narratives will be provided in the CSR for patients who have ALT $\geq 3x$ ULN plus Total bilirubin $\geq 2x$ ULN or AST $\geq 3x$ ULN plus Total bilirubin $\geq 2x$ ULN at any visit.

Liver biochemistry test results over time for patients with elevated ALT or AST (ie, $\geq 3x$ ULN), and elevated Total bilirubin (ie, $\geq 2x$ ULN) (at any time) will be summarized. Individual patient data where ALT or AST (ie, $\geq 3x$ ULN) plus Total bilirubin (ie, $\geq 2x$ ULN) are elevated at any time will also be listed.

3.3.9 Concomitant medication

Any medications taken by the patient at any time between the date of the first dose (including the date of the first dose) of study treatment up to the date of last dose of study treatment + 90 days in the study will be considered as concomitant medication. Any medication that ended prior to the first dose of the study treatment will be considered as prior medication.

3.3.10 Anti-cancer therapy

Anti-cancer therapy in the study will be classified as previous, concurrent and subsequent anti-cancer therapy. Previous anti-cancer therapy is the anti-cancer therapy which start before the first dose of study drug. Concurrent anti-cancer therapy is the anti-cancer therapy which start after the first dose of study drug and before the last dose of study drug. Subsequent anti-cancer therapy is the anti-cancer therapy which start after the last dose of study drug.

4 ANALYSIS METHODS

4.1 General principles

4.1.1 Analysis software

SAS[®] v9.4 or above version will be used for statistical analysis.

4.1.2 General analysis methods

All data, demography, baseline characteristics, safety, and efficacy, will be summarized using descriptive statistics, as appropriate for the type of data, for the SS. In addition, some efficacy and safety data will be summarised separately for the WHO/ECOG PS 0, 1 and 2 subgroups.

For continuous variable, no. of non-missing patients, no. of missing patients (nmiss), mean, standard deviation (Std), median, interquartile range (Q1 and Q3), maximum and minimum values will be used to descriptive the variable. The minimum and maximum will keep the same decimal place with the raw data, while mean, median, Q1 and Q3 will keep one more decimal place, and Std will keep two more decimal places. The decimal place of above statistics will not exceed four regardless of the decimal place of raw data.

For category variable, no. of patients and proportions will be adopted. "0" will be displayed when the count was zero. The proportions are all based on the non-missing data and will keep one decimal place unless otherwise specified. Two-sided 95% confidence intervals (CIs) will be provided as appropriate.

All patients who received at least one dose of study treatment will be included in SS, which will be the primary analysis set for all analyses unless otherwise specified.

4.1.3 Hypothesis test

No hypothesis test is required for the primary endpoints, which are descriptive.

4.1.4 Baseline

The baseline of all measurements and tests will use the latest valid records before first dose of study treatment.

4.1.5 Unscheduled visits

The records in unscheduled visits will be aligned with predefined terms of measurements and tests in the study. The results will be included in the shift table of these laboratory tests and measurements. The records in unscheduled visits will also be presented in listings but not summarized by visit.

4.1.6 Data derivation rules

The data derivation rules are describe as follows:

Table 5 Variable derivation rules

Variable (unit)	Definition	Derivation rules
Age (years)	Years from birth date to informed consent	Integer part of $((\text{date of informed consent} - \text{date of birth}) / 365.25)$
Time from first dose of study treatment to the date of disposition event (months)	Months from the date of first dose of study treatment to the start date of disposition event	$(\text{Start date of disposition event} - \text{date of first dose of study treatment} + 1) / 30.4375$, round to 2 decimal place
Time from original diagnosis to informed consent	Months from the date of original diagnosis to the date of informed consent	$(\text{Date of informed consent} - \text{date of original diagnosis}) / 30.4375$, round to 2 decimal place
BMI at each visit (kg/m ²)	Weight over squared height	Weight at each visit (kg) / height at screening (m) ² , round to 2 decimal place
Time from original diagnosis to the first	Months from the date of original diagnosis of SCLC	$(\text{Date of first dose of study treatment} - \text{date of original$

dose of study treatment (months)	to the date of first dose of study treatment	diagnosis of SCLC + 1) / 30.4375, round to 2 decimal place
Time from the latest assessment to the first dose of study treatment (months)	Months from the date of latest assessment of SCLC to the date of first dose of study treatment	(Date of first dose of study treatment – date of latest assessment of SCLC + 1) / 30.4375, round to 2 decimal place
Time to first AE (days)	Days from the date of first dose of study treatment to the date of first AE occurrence or censoring	Date of first AE or censoring – date of first dose of study treatment +1
Duration of AE (days)	Days from the AE start date to the AE stop date or date of DCO. The date used should not be imputed.	AE stop date or date of DCO – AE start date +1

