4.1.7 Handling of missing data and incomplete date

Missing safety data will generally not be imputed. However, safety assessment values of the form of “<x” (i.e. below the lower limit of quantification) or >x (i.e. above the upper limit of quantification) will be imputed as “x” in the calculation of summary statistics but displayed as “<x” or “>x” in the listings.

Additionally, adverse events that have missing causality (after data querying) will be assumed to be related to study drug, with the exception of causality assessments that are not applicable for the patient. The original incomplete or missing dates will be presented in the listings.

- Adverse events: all AEs will be considered as treatment-emergent unless the opposite can be clearly stated.
- Concomitant medications: all medications will be considered as concomitant unless the opposite can be clearly stated.

The original incomplete or missing start dates will be imputed as below:

- Missing day: impute the 1st of the month unless month is same as month of first dose of study drug then impute first dose date
- Missing day and month: impute 1st January unless year is the same as first dose date then impute first dose date

- Completely missing – impute first dose date unless the end date suggests it could have started prior to this in which case impute the 1st January of the same year as the end date.

When imputing a start date, ensure that the new imputed date is sensible i.e. is prior to the end date of the AE or study.

Partial AE or medication end dates will be imputed as follows:

- If only day is missing: impute day as the earlier of either the date of DCO or the last day of the month;
- If day and month are missing: impute day and month as the earlier of either the date of DCO or the last day of the year;
- If the end date is missing, then the analysis end date will not be imputed.

Imputed dates will not be used for deriving duration of events or treatment.

If a patient is known to have died where only a partial death date is available then the date of death will be imputed as the latest of the last date known to be alive +1 from the database and the death date using the available information provided:

- For missing day only – using the 1st of the month
- For missing day and month – using the 1st of January

If there is evidence of death but the date is entirely missing, it will be treated as missing, i.e. censored at the last known alive date.

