4.2.4 Primary endpoints

Adverse events, which start after first dose of study drug up to 90 days after the last dose of durvalumab treatment or the date of initiation of the first subsequent therapy, whichever occurs first, will be analysed in summary table. Other AEs recorded in the study will only be listed. This rule applies to all analysis of AE.

Frequency of AEs of CTCAE grade ≥ 3 , no. and percentage of patients with AEs of CTCAE grade ≥ 3 will be presented. These AEs will also be summarized by System Organ Class (SOC) and preferred term (PT). The exact 95% CIs around the incidence estimates will also be reported.

Time to event endpoints will be analysed using Kaplan-Meier method to estimate the median event time to the first AE of CTCAE grade 3 or higher. If a patient has no AE of CTCAE grade 3 or higher, the time to event will be censored at the date of DCO, death, 90 days after

the last dose of durvalumab treatment or the date of initiation of the first subsequent therapy, whichever occurs first. K-M curve will be presented.

Similar analyses will be conducted for imAEs.

An imAE is defined as an AESI that is associated with drug exposure and is consistent with an immune-mediated mechanism of action and where there is no clear alternate etiology. In general, imAEs will include AESIs that are managed using steroids, immunosuppressants and/or hormone replacement therapy.

The identification of imAEs will be made following the AstraZeneca imAE characterization charter.

1. The selection of preferred term,
2. Programmatic identification of those potential imAEs requiring medication such as steroids, immunosuppressants and/or hormone replacement therapy

All imAEs which are identified by the investigator (as recorded in CRF Adverse Events (AE)) will undergo a review by medical monitor. In addition, imAEs will be checked programmatically as described in the imAE charter on the clinical database to ensure the recording of imAEs are complete and unambiguous. If any discrepancies found, those will be resolved as an on-going basis and before DBL.

All above AEs will be listed.

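### Table 5 runs the duration of an AE without a stop date to the data cut-off with no cap at death or end of observation, so an unresolved AE can be given days after death

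*SAP*

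**What the plan says.** The duration row of Table 5 (SAP Section 4.1.6) gives the definition "Days from the AE start date to the AE stop date or date of DCO" and the formula "AE stop date or date of DCO – AE start date +1". The same cell adds "The date used should not be imputed".

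Section 4.1.7 has rules for partial AE end dates, but for a wholly absent one it says "If the end date is missing, then the analysis end date will not be imputed". It also says "Imputed dates will not be used for deriving duration of events or treatment".

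Section 3.2.9 has AEs collected from consent through treatment, "including the follow-up period up to 90 days after the last dose of durvalumab treatment". In Appendix A, AE monitoring is marked up to the safety follow-up visit and not for the survival calls.

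Section 4.2.4 treats the end of observation differently for time to first grade 3 or higher AE. For a patient without such an event, "the time to event will be censored at the date of DCO, death, 90 days after" the last durvalumab dose, or the start of the first subsequent therapy, taking the earliest. Similar analyses are planned for imAEs.

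Section 5 plans a primary analysis 6 months after LSI and a later final analysis.

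**The concern.** An AE that is still open when a patient dies, withdraws or has the last AE assessment has a known minimum duration and an unknown true one. Table 5 instead gives it a single number that ends at a calendar date unrelated to the patient. If the patient died before DCO, part of that number is time after death. If the patient is alive but no longer assessed for AEs, part of it is time in which the AE's status is unknown.

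Such records are to be expected: Section 4.2.6.1 includes a not-recovered outcome category, and Section 5 anticipates PFS maturity of about 60% at the primary analysis. The SAP does not say how many patients will have an unresolved AE when observation ends.

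The value also depends on when the database is cut. The same unresolved AE would have one duration at the primary analysis and a longer one at the final analysis, although nothing more had been recorded about it. A reader of a listing or table could not tell such a value from a duration with an observed end.

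**Working it through.** The SAP states no AE-duration figure, so there is nothing to reproduce. The check applies the Table 5 rule to illustrative patients.

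**Which branch applies.** With no stop date recorded, Section 4.1.7 leaves the end date missing. Table 5 offers only the stop date or DCO, so DCO is used. No section of the SAP limits this by death, withdrawal or last assessment.

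**Formulas.**
- Duration under Table 5 = DCO − AE start + 1
- Duration to end of observation = end of observation − AE start + 1
- Excess = DCO − end of observation (the start date cancels)

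**Inputs, all assumed except the formula.** Day 1 is the first dose and the AE starts on Day 30 with no stop date. DCO falls 6, 12, 18 or 24 months after this patient's first dose. At 30.4375 days per month, rounded, plus 1, these are Days 184, 366, 549 and 731. Six months is roughly the shortest interval if LSI means last subject in, which the SAP does not spell out. The longer intervals stand for earlier enrolment.

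- Patient A dies on Day 60. Duration to death = 60 − 30 + 1 = 31 days.
- Patient B is alive, and AE status was last recorded on Day 112 (for example, last durvalumab on Day 22, plus 90 days, with no later record). Duration to that date = 112 − 30 + 1 = 83 days.

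| DCO after first dose | DCO day | Table 5 duration | Excess, A (DCO − 60) | Excess, B (DCO − 112) |
|---|---|---|---|---|
| 6 months | 184 | 184 − 30 + 1 = 155 | 124 | 72 |
| 12 months | 366 | 366 − 30 + 1 = 337 | 306 | 254 |
| 18 months | 549 | 549 − 30 + 1 = 520 | 489 | 437 |
| 24 months | 731 | 731 − 30 + 1 = 702 | 671 | 619 |

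**Effect of a second cut-off.** If the primary DCO falls on this patient's Day 366 and the final DCO on Day 731 (both assumed), the recorded duration rises from 337 to 702 days. That is 365 days more, with no new AE information.

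**Comparison with Section 4.2.4.** For patient A without a qualifying event, time to first AE would be censored no later than death on Day 60. The duration row would carry patient A's open AE on to DCO. Both rules came in with the amendment of April 2022.

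**The case against.** **No planned analysis uses the variable.** The AE analyses in Sections 4.2.4, 4.2.5.7 and 4.2.6.1 cover incidence, frequency, grade, outcome, relatedness, deaths and time to first event. None summarises duration. This stands, and it is why the point is minor. A reader might infer that reported imAE durations, or a primary result, are distorted; the visible text does not support that. The mock shells and ADaM specifications are separate documents and may list or tabulate the variable.

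**DCO may be meant only as truncation.** The wording could be read to cover AEs still under observation at DCO, or stop dates after it, leaving an AE without a stop date in a patient who died with no duration. That reading is possible, but Table 5 does not state it. A programmer following the formula would use DCO for any absent stop date.

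**The imputation bar.** A reader might infer that Table 5 contradicts itself, since substituting DCO resembles an imputation and imputed dates are barred from durations. The documents do not establish this. Table 5 names DCO in the same cell as the bar, and Section 4.1.7 speaks of completing partial or missing dates. The two can be read together, and the point does not need a contradiction.

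**Follow-up of open AEs.** A reader might infer that nothing is known about any AE beyond 90 days past the last durvalumab dose. Section 3.2.9 says when AEs are collected, not that follow-up of an AE already recorded stops then. A fixed 90-day cap could discard real observations. Closing AEs on the CRF at death would also remove the post-death part, but this SAP states no such convention.

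**The sizes are illustrative.** The dates are assumed, and any ratio of the two durations depends on them. What holds generally is that the excess equals DCO minus the end of observation.

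**Conclusion.** The point holds as a minor error in a stated rule. As written, Table 5 gives an AE with no stop date a duration to DCO even when the patient died, withdrew or was last assessed earlier. The SAP's own AE censoring rule in Section 4.2.4 does stop at death and at the end of the AE window, so the two AE time variables treat the end of observation inconsistently.

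The excess per AE is 124 to 671 days for a death on Day 60, and 72 to 619 days for a last recorded status on Day 112, with DCO 6 to 24 months after first dose. These ranges rest on the assumed dates, on no stop date having been entered at death or study exit, and on the literal reading of the formula. The number of AEs affected cannot be derived from the SAP.

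The impact is confined to the derived duration and any listing or table that uses it. The incidence endpoints, time to first AE and the efficacy endpoints do not use it.

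**What to change.** In the duration row of Table 5, state that an AE with no stop date ends at the earliest of DCO, death, and withdrawal or last recorded AE status. Flag that duration as censored, and show it as at least x days wherever it is listed or summarised. State that DCO is a permitted end date under this row, so that the bar on imputed dates is not read as excluding it.

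The list in Section 4.2.4 need not be copied in full. Start of subsequent therapy and the 90-day limit bound the window for counting AEs, whereas an AE already recorded may still be observed afterwards. The last recorded status covers that case.

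The cost is one line in Table 5, the matching line in the ADaM specification, and a censoring flag. Death, visit and disposition dates are already used for OS in Section 3.2.7. No new data collection or new analysis is needed; a Kaplan-Meier summary of duration would go beyond what this correction requires.
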